4.5. Treatment Assignment Procedures

4.5.1. Randomization procedures

A permuted block randomization method with 1: 1: 1 :1 ratio will be employed to allocate subjects into one of the four treatment arms as follows (1) Antroquinonol 150 mg PO QD; (2) Antroquinonol 100 mg PO QD; (3) Antroquinonol 50 mg PO QD; or (4) Placebo arm. Randomization code list will be generated by the CRO and provided to Golden Biotechnology Corporation in order to pack and label the study drugs. Randomization data will not be accessible by anyone else involved in the study. The corresponding study group of individual subjects will be recorded in a sealed envelope and should be kept strictly confidential until the time of data lock.

For this multi-center study, centralized randomization will be applied. The investigator confirms the subject fulfills the inclusion and exclusion criteria and informs the randomization center. The sponsor's independent staff will then provide the randomization number in order. The study drugs labeled with randomization number will be provided according to the request from each site.

4.5.2. Blinding procedures

After enrollment, subjects will be randomly assigned to receive one of the study treatments in a double-blind fashion. The identity of the treatments will be concealed. The placebo will be masked by the same appearance, odor and taste as the study drug (Antroquinonol). Subjects,

investigator, site staff, persons performing study assessments and data analysts will remain blind to the treatment assignment from the time of randomization until data lock.

All patients enrolled should take 3 capsules within 15 minutes after the first meal every day. In the study group, subjects will be treated with (1) 3* Antroquinonol 50 mg capsule; (2) 2* Antroquinonol 50 mg capsule and 1 capsule of placebo; (3) 1* Antroquinonol 50 mg capsule and 2 capsules of placebo and (4) in the control group, subjects will be treated with 3 capsules of placebo.

The blinding during the study is maintained by administration of matching placebo capsules to patients in the placebo group. Furthermore, the project teams of Golden Biotechnology Corporation and the CRO as well as the investigator and his/her study personnel will be blinded with respect to patients' assignment to one of the four treatment groups.

Treatment codes should not be broken except in the case of emergency situations. If the investigator wishes to know the identity of the treatment given to study patients for any other purpose, this request should first be discussed with Golden Biotechnology Corporation.

As per regulatory reporting requirement, Golden Biotechnology Corporation will unblind the identity of the study medication for all unexpected (as per the Investigator Brochure [IB]) serious adverse events that are considered by the investigator to be related to study drug. Details of patients who are unblinded during the study will be included in the Clinical Study Report.

All other individuals directly involved in this study will remain blinded until the final analysis of the primary parameter.

4.5.3. Subject identifier

Each subject will be assigned a consecutive numbers as he/she enters the study. In the study, the screening and randomization numbers are used as subject identifiers. The subject who signed the informed consent form will be assigned a sequential screening number starting with an alphabet "S" and following with 3 digits at visit 1 (Screening visit) by each site. The subject who meet the eligible criteria will be enrolled and granted a random number by randomization process before visit 2. The random number is composed of 3 digits and an initial alphabet "R". Once assigned to a subject, the screening numbers at each site and randomization numbers will not be reused. This random number will be used to identify the subject throughout the clinical study and must be used on all study documentation related to that subject. A two-digit site number will also be indicated on case report form as well as related working sheets. In that case, National Taiwan University Hospital will be coded as site "01". Once a new institution participates in the present study, the site number will be increased sequentially, e.g. site "02" for the second institution.

4.5.4. Reasons for withdrawal

Subjects may be discontinued from study drug at the discretion of the investigator of any untoward effects occur or for one of the following reasons:

- (1) Subject who cannot comply with the medical practices and the schedule of follow-up visit;
- (2) Subjects (or their legally acceptable representatives, if applicable) decide to withdraw their informed consent forms;
- (3) Investigator considers that the subject is no longer physically or psychologically feasible to be included in this study;
- (4) Adverse effects occur in subjects that the investigator considers a permanent cessation of the study treatment is necessary;
- (5) Violation of enrollment criteria which is not recognized at the time of enrollment;
- (6) Lost to follow-up;
- (7) Lack of response to study treatment and the investigator considers that the subject shall be withdrawn to receive other treatments.

Subjects who are withdrawn because of lost to follow-up will be contacted by telephone, and the information will be recorded on the "Study Termination" of Case Report Form (CRF), including the date of the event and the reasons for not returning to the clinic by study staff.

4.5.5. Handling of withdrawals

Subjects have the right to withdraw from the study at any time for any reason. The investigator also has the right to withdraw patients from the study in the event of intercurrent illness, adverse events, protocol violations, administrative reasons or other reasons. An excessive rate of withdrawals can render the study un-interpretable; therefore, unnecessary withdrawal of patients should be avoided. Should a patient decide to withdraw, all efforts will be made to complete and report the observations prior to withdrawal as thoroughly as possible.

The investigator should contact the subject or a responsible relative either by telephone or through a personal visit to establish as completely as possible the reason for the withdrawal. A complete final evaluation at the time of the subject's withdrawal should be made with an explanation of why the subject is withdrawing from the study. If the reason for removal of a subject from the study is an adverse event, the principal specific event will be recorded on the case report form (CRF).

Subjects withdrawing from the study should be followed for occurrence of adverse events unless the patient refuses to give further information.

Any subjects withdraw from the study, the study staff shall inform the sponsor and CRO within 5 working days.

4.5.6. Termination of study

This study may be prematurely terminated if, in the opinion of the investigator, the sponsor or due to health authority's review, there is sufficient reasonable cause. Written notification, documenting the reason for study termination, will be provided to the investigator or sponsor by the terminating party.

5. STUDY DRUG/INTERVENTION

5.1. Description of Study Drug

5.1.1. Drugs manufacture and supplier

The study drug Antroquinonol is provided and manufactured by Golden Biotechnology Corporation. The matching placebo of Antroquinonol used during the study will also be supplied by Golden Biotechnology Corporation.

5.1.2. Formulation, packaging and labeling

Antroquinonol will be provided as a 50 mg capsule. Study drug is capsule-shaped, identical in appearance to placebo. The study drug and matching placebo will be packaged as Antroquinonol with appearance identical in all aspects. The study drug will be packaged in a light-proof polypropylene pill box and will be labeled with following information:

- Sponsor identification
- Manufacturer
- Protocol number
- Randomization number
- Quantity of contents
- Prescription instructions
- Storage conditions
- Expiration date
- Caution statements:
“FOR CLINICAL TRIAL USE ONLY”
“KEEP OUT OF REACH OF CHILDREN”
- Blank spaces to write the data while dispensing.

Detailed instructions and training for the administration of study supplies will be provided by investigator or designees of the study site.

5.1.3. Product storage and stability

The study drugs will be handled by the investigator or the designated pharmacist for management and dispensation. The storage area for study drugs at the site must be monitored by the site staff for temperature consistency with the acceptable storage temperature range specified in this protocol or in the product label. Documentation of temperature monitoring should be maintained. Importantly, the study drug supplied for this study must be maintained under adequate security and stored under the conditions specified on the label until dispensed for subject use or returned to Golden Biotechnology Corporation.

The optimal storage condition for study drugs is described as below:

The individually labeled double-blind study medication kits should be kept under 28°C, away from moisture and heat in a cool place away from light. The study drug supplies should be stored in a locked and secure area with limited access.

5.2. Dosage, Preparation and Administration of Study Drug

Participants will receive medication supplies at scheduled visits in sufficient quantity until the next scheduled visit. Patients will take their daily dose of Antroquinonol and/or placebo as follow: in the study group, subjects will be treated with (1) 3* Antroquinonol 50 mg capsule; (2) 2* Antroquinonol 50 mg capsule and 1 capsule of placebo; (3) 1* Antroquinonol 50 mg capsule and 2 capsules of placebo within 15 minutes after first meal every day; and in the control group, subjects will be treated with 3 capsules of placebo within 15 minutes after meal every day.

5.3. Modification of Study Drug for a Subject

No modification of dose will be conducted in the present study. If any drug toxicity occurs to the subject, he/she may be withdrawn from the study by the investigator's determination.

5.4. Accountability Procedures and Assessment of Subject

Compliance for the Study Drug(s)

Accountability and subject compliance will be assessed by maintaining adequate drug dispensing and return records.

Patients will be asked to return all used and unused drug supply containers from visit 3 to visit 5 as a measure of compliance.

Drug record section on CRF and drug dispensing logs must be kept current and should contain the following information:

- the identification of the subject to whom the study medication was dispensed
- the date[s], quantity of the study medication dispensed to the subject
- the date[s] and quantity of the study medication returned by the subject

This inventory must be available for inspection by the Monitor. All supplies, including partially used or empty containers and the dispensing logs, must be returned to the Golden Biotechnology Corporation or Golden Biotechnology Corporation designee at the end of the study. The investigational staff must record quantity of medication dispensed and returned on

CRF. In addition, a dispensing log for each subject shall also be completed by the staff. This dispensing log will be supplied to the institution before study initiation. The log will include the subject's identification, drug lot/batch number, dispensed and returned date and quantity, signature of site staff, comments which is used to record any unusual situation and verification section by CRO,

5.5. Treatment for Study Drug Overdose

The effects of overdose of study drug are under investigation. Per the phase I and ongoing phase II study in oncology patients, no single event of overdose is recorded. In the event of overdose, standard measures to remove any unabsorbed drug should be considered. Symptomatic and supportive treatment is recommended.

5.6. Concomitant Medications/Treatments

5.6.1 Prohibited medications/treatments

The following treatments are not permitted during the study

- Statin therapy,
- Steroids,
- Fibrates,
- Anti-lipid medication

Patients will also be informed that they should avoid foods including broccoli, Brussels sprouts, charbroiled food, cruciferous vegetables, star fruit, and grapefruit juice within four hours after taking Antroquinonol. Cigarette smoking is also prohibited during the study.

5.6.2 Permitted medications/treatments

Throughout the study, investigators may prescribe any concomitant medications or treatments deemed necessary to provide adequate supportive care which does not affect serum lipid level except for those listed in Section 5.6.1.

6. STUDY PROCEDURES

This is a, randomized, double-blind, placebo-controlled study composed of the following:

- (1) a screening visit including a wash-out period of 2 weeks will be applied to patients prior to the treatment of Antroquinonol;
- (2) randomization of subjects who meet the eligibility criteria in 1: 1: 1 :1 ratio into the four treatment groups (Antroquinonol 150 mg, Antroquinonol 100 mg, Antroquinonol 50 mg or placebo);
- (3) three on-treatment visits scheduled at four-week interval during which efficacy and safety assessments will be performed;
- (4) and a follow-up visit after the end of treatment, during which safety assessments will be performed.

6.1. Flow Chart

Scheduled examination components are shown by visit in Tables below, all of the assessments are indicated with an “X” at the visits when they will be performed.

STUDY SCHEDULE:

Procedure	Screening *	Randomization	Treatment Period			Follow-up
Visit	Visit 1	Visit 2	Visit 3	Visit 4	Visit 5	Visit 6
Interval	Day -14 (Week 1)	Day 1 (Week 1)	Day 29 (Week 5)	Day 57 (Week 9)	Day 85 (Week 13)	Day 99 (Week 15)
Allow Window	-	-	±3	±3	±3	±3
Informed Consent	X					
Assessment of Eligibility Criteria	X					
Medical History	X					
Demographic	X					
Vital Signs ¹	X	X	X	X	X	X
Anthropometric measures ²	X	X	X	X	X	X
Electrocardiogram		X			X	
Physical Examination	X	X	X	X	X	X
Urine Pregnancy Test	X					
Randomization ³		X				
Drug Dispense		X	X	X		
Drug Return			X	X	X	
Efficacy Assessment						
Serum Lipid ⁴	X	X	X	X	X	X
baPWV and ABI		X			X	
Image Monitoring ⁵		X			X	
Biomarker Assessment						

Procedure	Screening *	Randomization	Treatment Period			Follow-up
Visit	Visit 1	Visit 2	Visit 3	Visit 4	Visit 5	Visit 6
Interval	Day -14	Day 1 (Week 1)	Day 29 (Week 5)	Day 57 (Week 9)	Day 85 (Week 13)	Day 99 (Week 15)
Allow Window	-	-	±3	±3	±3	±3
CRP and Cytokine ⁶		X			X	X
Safety Assessment						
CBC and WBC differential ⁷		X			X	X
Biochemistry ⁸	X	X	X	X	X	X
Urinary Exam ⁹		X			X	X
Concomitant Therapy	X	X	X	X	X	X
Adverse Event		X	X	X	X	X

* A wash-out period of 2 weeks will not be applied to patients prior treated with medication which does not affect serum lipid level.

1. Vital signs: pulse rate, body temperature, respiratory rate, and blood pressure (including systolic blood pressure (SBP) and diastolic blood pressure (DBP)).
2. Including height, weight, waist circumference, and BMI (calculated by kg/m²)
3. Subjects who meet the eligibility criteria will be randomized into treatment arms. If the eligibility is confirmed and a wash-out period is not needed for the subject, based on investigator's judgements the blood test required at V2 can be replaced by the data obtained 14 days before V2.
4. Serum lipids: total cholesterol, triglycerides, HDL-C, LDL-C, LDL/HDL ratio. **Serum lipid results obtained 3 days prior to V1 is acceptable.**
5. Doppler color flow mapping and CT scan of the liver. CT scan will not be scheduled at visit 5 on subjects without fatty liver. **Results of Doppler color flow mapping and CT scan of the liver obtained between V1 and V2 are acceptable.**
6. hsCRP, IL-1, IL-6, and TNF-alpha.
7. WBC, RBC, Hb, Hct, RDW, platelet, MCV, MCH, MCHC, neutrophil-band and segment, lymphocyte, monocyte, eosinophil, and basophil.
8. Biochemical exam: AST, ALT, CPK, BUN and serum creatinine: visit 2 to visit 6; albumin, total bilirubin, direct bilirubin, ALP, total protein: V2, V5 and V6. At screening visit, serum creatinine shall be run for estimating glomerular filtration rate (GFR) **and data obtained 3 days prior to V1 is unacceptable.**
9. Urinary exam: routine urine test (pH, protein, glucose, ketone, blood, urobilinogen, bilirubin, nitrite, leukocyte) and clinical microscopy.

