4.2. Inclusion Criteria

Subjects are eligible if the following inclusion criteria are satisfied:

- (1) Adults of either sex 20 to 75 years of age, inclusive, with a diagnosis of nonfamilial hypercholesterolemia or mixed hyperlipidemia as one of the following:
 - TG between 150 mg/dL and 500 mg/dL, and cholesterol between 160 mg/dL and 250 mg/dL
 - TG between 150 mg/dL and 500 mg/dL and LDL-C > 130 mg/dL);
- (2) Subject must be free of any clinically significant disease, other than nonfamilial hypercholesterolemia or mixed hyperlipidemia that would knowingly interfere with study evaluations;
- (3) A wash-out period of 2 weeks will be applied to patients prior treated with lipid-lowering medication;
- (4) Subject must be willing to adhere to protocol requirements, and provide written informed consent;
- (5) Female of child-bearing potential must agree to use adequate contraception (hormonal or barrier method of birth control; abstinence) prior to study entry and for the duration of study participation.

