6.2. Study Procedures

6.2.1. Screening (Day -14)

All patients must provide written informed consent before any study specific assessments or procedures are performed. A subject enrollment form documenting the investigator's assessment of each screened subject with regard to the protocol's inclusion and exclusion criteria has to be completed by the investigator.

Based on the results of Visit 1 assessments (see below 'Screening Assessments at Visit 1'), potentially eligible patients will enter a wash-out period as necessary. Blood test data generated by the study site or central laboratory 3 days prior to Visit 1 can be accepted.

Screening Assessments at Visit 1

- Demographics, medical history, including previous and concomitant diseases and treatments
- Physical examination
- Anthropometric measures (Height, Weight, Waist circumference, BMI)
- Vital signs (pulse rate, body temperature, respiratory rate, and blood pressure)
- Urine Pregnancy Test
- Blood samples for
 - lipid profile (total cholesterol, TG, HDL-C, LDL-C and LDL/HDL ratio)
 - biochemistry (serum creatinine for estimating GFR)

Patients will be instructed to come in fasted state for all subsequent study visits. Patients should receive information on a heart healthy diet and counseling on lifestyle changes as appropriate.

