6.2.2. Enrollment/Randomization (Day 1)

Randomization Assessments at Visit 2

Once a patient has fulfilled the entry criteria, he/she will be randomized into either Antroquinonol 150 mg, Antroquinonol 100 mg, Antroquinonol 50 mg or placebo treatment group using a permuted block randomization method with 1: 1: 1: 1 ratio. The subject will be registered with a randomization number, and the study drug will be administered. The importance of compliance with study drug should be emphasized.

The assessments listed below will be performed. If the eligibility is confirmed and a wash-out period is not needed for the subject, based on investigator's judgements, the blood test, CT Scan, and Doppler color flow mapping required at visit 2 can be replaced by data obtained 14 days before V2.

- Physical examination
- Anthropometric measures (Height, weight, waist circumference, BMI)
- Vital signs (pulse rate, body temperature, respiratory rate, and blood pressure)

- Blood samples for
 - lipid profile (total cholesterol, TG, HDL-C, LDL-C and HDL-C /LDL-C ratio)
 - hematology (WBC, RBC, Hb, Hct, RDW, platelet, MCV, MCH, MCHC, neutrophil-band and segment, lymphocyte, monocyte, eosinophil, basophil)
 - serum chemistry (AST, ALT, CPK, BUN, serum creatinine, albumin, total bilirubin, direct bilirubin, ALP, total protein)
 - biomarkers (hsCRP, IL-1, IL-6, and TNF-alpha)
- 12-lead electrocardiogram
- Brachial-ankle pulse wave velocity (baPWV) and ankle-brachial index (ABI)
- Doppler color flow mapping, and CT scan of the liver
- Urinalysis
 - routine urine test (pH, protein, glucose, ketone, blood, urobilinogen, bilirubin, nitrite, leukocyte)
 - clinical microscopy

In addition, information on adverse events during the wash-out period and new concomitant medications will be collected.

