7.5.2 Specimen preparation, handling, and storage

The blood and urine samples will be examined at Union Clinical Laboratory in line with the SOPs during the study. **The blood and urine samples will be examined at the site laboratory as well only for eligibility measurement at screening visit.**

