9.4. Analysis Plan

General data analysis

For continuous endpoints, descriptive statistics including number, mean, median, standard deviation, minimum, maximum, and 95% confidence intervals will be presented. Continuous variables will be analyzed by means of ANOVA with Bonferroni adjustment. Paired T-Test will be used to compare the change from baseline within treatment groups. If the data strongly indicate a violation of the normal assumption, the non-parametric method of Kruskall Wallis test or Wilcoxon Signed-Rank Test will be applied for analysis.

For categorical endpoints, the count and percentages will be used to summarize the categorical data. The Chi-square test will be performed to test the difference between groups while Fisher's exact test will be applied for any counting of the frequency is less than 5.

All statistical analyses will be conducted using SAS software.

Endpoints

The primary efficacy endpoint for assessing the superiority of Antroquinonol to placebo will be analyzed using analysis of covariance (ANCOVA) model and baseline measurement as covariates, if the differences in baseline characteristics, such as gender, age, weight etc., are observed, for comparing the effectiveness between the treatment groups.

Analysis of other secondary efficacy endpoints (TC, HDL-C, LDL-C, and LDL/HDL ratio as well as the effect of Antroquinonol on E/E', baPWV and ABI and HU parameters) will be similar to the primary analysis of the primary endpoint. All tests will be based on a significance level of 0.05, without adjustment for multiple endpoints.

For the safety assessments, the information of adverse events will be described in detail. Count

and percentage will be tabulated for the number of patients with AEs, number of total AEs, number of patients with AEs associated to study dosing and intensity. Adverse events will be coded by the Medical Dictionary for Regulatory Activities (MedDRA®) adverse event dictionary. All the AEs will be categorized by each represented Preferred Terms (PT) and System Organ Class (SOC), which will be tabulated by body system with related incidence rates. The clinical laboratory tests and electrocardiogram tests will be analyzed to separate subjects into normal and abnormal categories, with number of subjects and percentage of subjects in each category, and McNemar's test or Fisher's exact test will then be applied to test the changes between each visit.

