**Protocol: GHLIP-2-001**

**Study Sponsor: Golden Biotechnology Corporation**

additional variables will be required. The SAP will not be amended for additional variables that are not related to the primary endpoint or key secondary endpoints. An additional derived or computed variables will be identified and document in the SAS programs that create analysis files.

- Age (years) = (date of giving informed consent – date of birth)/365.25
- BMI (kg/m^2) = Weight (kg) / Height (m^2)
- Treatment Compliance (%) =  $\frac{\text{Quantity of total dispensed} - \text{Quantity of total returned}}{\text{Treatment period (84 days)}} \times 100\%$
- Percentage change from baseline of TG (%) =  $\frac{\text{Day85 (TG)} - \text{Day1 (TG)}}{\text{Day1 (TG)}} \times 100\%$

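### The triglyceride value that qualified the patient at screening may replace the Day 1 baseline, so arm-level change and the within-group tests can show a fall with no drug effect

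*Protocol*

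**What the plan says.** **Substitution.** Protocol 6.1, footnote 3, covers a patient whose eligibility is confirmed and who needs no wash-out. At the investigator's discretion, "the blood test required at V2 can be replaced by the data obtained 14 days before V2". Protocol 6.2.2 says the same of the Visit 2 bloods and imaging ("can be replaced by data obtained 14 days before V2"), above a list of blood samples that starts with the lipid profile. Footnote 3 of the SAP flow chart (4.1.1) repeats it. None of the three exempts lipids.

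**Where the replacement comes from.** Day -14 is the screening visit, whose lipid result decides entry. Protocol 4.2 requires "TG between 150 mg/dL and 500 mg/dL, and cholesterol between 160 mg/dL and 250 mg/dL", or the same TG range with LDL-C above 130 mg/dL.

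**Endpoint.** SAP 7.6 defines "Percentage change from baseline of TG" as Day 85 minus Day 1, divided by Day 1. It does not say what Day 1 means when that test was replaced.

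**Conditions of the screening sample.** At Visit 1, Protocol 6.2.1 says "Patients will be instructed to come in fasted state for all subsequent study visits". Protocol 6.2.3 requires fasting at all visits, but under the on-treatment heading. Protocol 6.2.1 also says "Blood test data generated by the study site or central laboratory 3 days prior to Visit 1 can be accepted". Protocol 7.5.2 names one study laboratory and adds: "The blood and urine samples will be examined at the site laboratory as well only for eligibility measurement at screening visit". Diet and lifestyle counselling is given at Visit 1.

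**Within-group tests.** Protocol 9.4 states "Paired T-Test will be used to compare the change from baseline within treatment groups". The Protocol Summary and SAP 9.2 plan the same test, with the signed-rank test as fallback.

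**The concern.** Two kinds of baseline enter one endpoint. A Day 1 value is an independent repeat measurement. A screening value is the measurement on which the patient was selected, so on average it tends to be too high and the next value falls back. Counselling after Visit 1 pushes in the same direction, and so would a non-fasting sample if it reads higher. Patients who had a wash-out cannot use the substitution, so the meaning of baseline also depends on prior treatment and on the investigator's choice.

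At stake are the reported TG reduction in each arm, which readers tend to quote, and the planned paired tests. Both could suggest lowering where there is none.

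**Working it through.** **1. What the substitution reaches.** Visit 1 schedules only the lipid panel and serum creatinine (Protocol 6.2.1). Lipids are therefore almost all that scheduled Visit 1 data can replace.

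**2. Selection alone, no drug effect.** From the documents: entry window 150-500 mg/dL (Protocol 4.2) and 24 evaluable per arm (Protocol 9.2; 24/0.80 = 30, and 30 x 4 = 120 enrolled). Assumed, because the documents are silent: the median TG of referred patients (150, 200 or 250 mg/dL), the between-person SD of log TG (0.3-0.4), the within-person SD (0.20-0.28), and the share of baselines replaced.

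The model is log TG = person mean + independent visit error, with patients kept if the screening value lies in the window and no true change. Baseline is the screening value in the replaced share and the Day 1 value otherwise. The test is a paired t-test of Day 85 minus baseline. The table gives the proportion of arms with a significant fall (nominal 2.5%).

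| Referral median (mg/dL) | None replaced | Half replaced | All replaced |
|---|---|---|---|
| 150 | 2-3% | 8-9% | 19-24% |
| 200 | 2-3% | about 4% | 6-7% |
| 250 | 2-3% | 2-3% | 2-3% |

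The half and all columns pair the SDs as 0.3 with 0.20 and 0.4 with 0.28. Crossing all four combinations widens the last column to 15-32%, 5-9% and 2-3%, and the half-replaced range to 2-11%. At a median of 250 few patients lie near the lower limit and the upper limit of 500 trims high values, so the effect vanishes.

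**3. Percentage scale.** A ratio of two noisy values has mean exp(within-person variance). With a true Day 1 baseline and no effect, mean percentage change is already exp(0.20²) - 1 = +4% to exp(0.28²) - 1 = +8%. At a median of 200 with all replaced it is about -0.3% to +0.9%. At a median of 150 (between-person SD 0.40, within-person CV 15-30%) it moves from between +2.2% and +8.9% to between -2.0% and -5.6%.

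**4. If the screening sample also reads high by a factor f (assumed).** An unchanged patient shows 1/f - 1, which is -9.1% at f = 1.10 and -16.7% at f = 1.20. With all replaced, medians of 150 and 200 and CV 20-30%, the two-sided paired t-test (nominal 5%) rejects in 24-62% of null arms at +10% and 54-93% at +20%. With half replaced at +10% it rejects in 9-20%.

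**5. Between arms.** ANCOVA with baseline TG, four arms of 24, median 150, CV 20% and 30%: type I error is 4.5-5.2% for any share replaced. The estimate moves somewhat. Take the 27.5% reduction in Protocol 9.2 as a proportional effect; the arm difference is then 27.5 times the mean null ratio of Day 85 to baseline.

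- Day 1 baseline: 27.5 x 1.04 = 28.6 and 27.5 x 1.09 = 30.0 points.
- All replaced, no offset: 27.5 x 0.968 = 26.6 and 27.5 x 0.942 = 25.9 points.
- Pure offset, all replaced: 27.5/1.10 = 25.0 and 27.5/1.20 = 22.9 points.

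**The case against.** The strongest reply is that the primary hypothesis and analysis compare randomised arms, with baseline TG as covariate (SAP 9.1, 9.3). Replacement is decided before treatment and under blinding, so it is not tied to arm, and any common shift also appears in the placebo arm. This stands. The within-group tests are supplementary and carry no success criterion.

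Four stronger readings are tempting, and the documents do not support them.

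- *The primary endpoint cannot be computed for these patients.* The SAP carries the same substitution, so the replaced value supplies the Day 1 input. What is missing is an explicit definition.
- *The within-group tests are invalid.* Step 2 shows that inflation from selection ranges from none to substantial, depending on a referral median and a replaced share that nobody has stated.
- *The baseline is a non-fasting value.* Protocol 6.2.1 is silent on fasting at Visit 1, and 6.2.3 can be read as covering every visit. The offsets in step 4 are therefore illustrations.
- *The baseline is a site-laboratory value.* Protocol 7.5.2 limits site testing to eligibility and implies that the study laboratory also tests screening samples. Results from 3 days before Visit 1 fall at about Day -17 on the nominal schedule, outside the 14 days. But footnote 3 names no laboratory, so the passages still need reconciling.

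Two further points stand in part. On the mean percentage scale the shift can cancel the upward artefact in step 3, but the paired test on TG change gets no such relief. Replacement may also be rare, because haematology, liver enzymes and biomarkers are first drawn at Visit 2. That makes the remedy nearly free.

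**Conclusion.** The point holds as a moderate one that should be fixed. A stated rule lets the qualifying screening TG serve as baseline in some patients, while the endpoint formula names Day 1 and no text reconciles the two. Arm-level change and the within-group tests can then show TG lowering with an inert drug.

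From selection alone the inflation is material if referred patients centre near the entry limit and replacement is common. It is slight at a median of 200 mg/dL and absent at 250. These figures rest on log-normal TG, the assumed SDs, 24 per arm and no offset. A real fasting or laboratory offset would dominate them, but the documents do not establish one.

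The randomised test of Antroquinonol against placebo is not in doubt. Its estimate could shrink modestly.

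**What to change.** - Exempt the lipid panel from the substitution in Protocol 6.1 (footnote 3), Protocol 6.2.2 and the SAP flow-chart footnote. Other Visit 2 blood tests may keep it.
- Draw a fasting lipid sample for the study laboratory at Visit 2, before the first dose, in every patient, and define that value as baseline TG in SAP 7.6.
- Where substitution has already occurred, flag those patients and add a sensitivity analysis of the primary endpoint restricted to true Day 1 baselines.
- Label the within-group tests as descriptive.
- Reconcile the fasting statements (Protocol 6.2.1 and 6.2.3) and the laboratory statements (Protocol 6.2.1 and 7.5.2).

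The cost is one lipid sample, at a visit that already takes place, for patients who would have skipped it, plus wording in both documents.
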